7.1 Safety Review Committee

A Safety Review Committee (SRC) will be convened and will include the medical monitor, the safety manager(s), clinical monitor(s) and clinical manager. The SRC will oversee safety data (AEs, vitals, clinical labs, ECG data, etc.) generated by enrolled study subjects on the trial. In addition, they will review all SAEs and UADEs and clinically significant safety observations noted during the study. Oversight work will be performed in accordance with a written Safety Review Committee Plan.

7.2 Assessment of Causality

The casual relationship to the study procedures and the investigational device for each adverse event will be related as follows:

- Unrelated: Clinical event with an incompatible time relationship to study device or study drug, and that could be explained by underlying disease or other drugs or is incontrovertibly not related to the study device.
- Unlikely: Clinical event whose time relationship to study device investigational drug makes a causal connection improbable, but that could plausibly be explained by underlying disease or other drugs.
- Possible: Clinical event with a reasonable time relationship to study device or investigational drug, but that could also be explained by concurrent disease or other drugs.
- Very Likely/Certain: Clinical event with plausible time relationship to study device or investigational drug, and that cannot be explained by concurrent disease or other drugs.

7.3 Assessment of Severity

The severity of the adverse events will be rated based upon the following grades:

- Mild: results in minimal transient impairment of a body function or damage to a body structure and/or does not require any intervention other than monitoring or OTC medication.
- Moderate: Results in moderate transient impairment of a body function or transient damage to a body structure and/or requires intervention, such as administration of medication or transfusion or

Statistical Analysis Plan		Page 24 of 29
MediBeacon Inc.	An Open Label, Multi-Center, Safety and Pharmacokinetic Bridging Study of MB-102 (Relmapirazin) and the Use of the MediBeacon [®] Transdermal GFR Measurement System using the TGFR Reusable Sensor with Disposable Adhesive Ring in Normal and Renal Compromised Subjects for the Evaluation of Kidney Function	Ver 4.0

laparoscopic or endoscopic procedure to prevent permanent impairment of a body function or damage to a body structure.

Severe: An event which is life threatening, results in permanent impairment of a body function or permanent damage to a body structure or necessitates significant intervention, such as major surgery, to prevent permanent impairment of a body function or permanent damage to a body structure. The term severe is often used to describe the intensity (severity) of a specific event (as in mild, moderate, or severe myocardial infarction); the event itself, however, may be of relatively minor medical significance (such as severe headache). This is not the same as serious, which is based on patient/event outcome or action criteria usually associated with events that pose a threat to a patient's life or functioning. Seriousness (not severity) serves as a guide for defining regulatory reporting obligations. An event that changes in severity (gets worse or gets better) should be noted as its worst severity.

7.4 Action Taken

The investigator will describe the action taken in the appropriate section of the eCRF, as follows:

- None
- Concomitant interventional treatment(s) administered (includes medications or procedures)
- ➢ Other, specify

7.5 Outcome of the Event

The investigator will describe the outcome of the event in the appropriate section of the eCRF, as follows:

- > Unknown
- ➢ Resolved
- > Ongoing
- Resolved with sequelae
- Death (with date and cause reported)

7.6 Evaluation of Device Malfunctions

Device malfunctions will be tabulated and listed in a manner similar to the methods described for adverse events. Any device malfunction leading to an adverse event or study termination will be listed separately.

Statistical Analysis Plan		Page 25 of 29
MediBeacon Inc.	An Open Label, Multi-Center, Safety and Pharmacokinetic Bridging Study of MB-102 (Relmapirazin) and the Use of the MediBeacon [®] Transdermal GFR Measurement System using the TGFR Reusable Sensor with Disposable Adhesive Ring in Normal and Renal Compromised Subjects for the Evaluation of Kidney Function	Ver 4.0

8 General Statistical Considerations

8.1 Analysis Sets

The following analysis populations will be defined for the study:

- Intent-to-Measure (ITM) Population The ITM population will consist of all subjects who are enrolled in the study in Stratum 1 & 2 and for whom an average session tGFR or an average snapshot tGFR* has been calculated, and who have not had any major protocol deviations that would impact TGFR system performance.
- Modified Intent-to-Measure (mITM) Population The mITM population will consist of all subjects in the ITM population with no outlier PK parameters.
- Safety Population The safety population will consist of all subjects who are enrolled in the study and have been dosed with MB-102.
- Pharmacokinetic (PK) Population The pharmacokinetic population will consist of all subjects who are enrolled in the study and have any PK data.

* Note: this includes short gaps in data that are less than 30 minutes due to a resumption of the monitoring session where an "average snapshot GFR" is reported instead of an "average session GFR".

The mITM population will be the primary analysis set for all effectiveness analyses. The Safety Population will be used for the analysis of all safety variables and baseline characteristics. The PK Population will be used for the analyses of PK data.

The ITM and mITM populations will be analyzed from subjects enrolled in the Validation 2 and Validation 3 (if applicable) cohorts only.

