5.4 Selection of Study Population

5.4.1 Number of Planned Evaluable Subjects

The study may enroll up to 240 subjects across 4 consecutive cohorts in order to obtain 140 evaluable subjects. Unevaluable subjects are those with major protocol deviations that impact efficacy (such as no reported average session tGFR, premature sensor removal, extravasations, etc.). The cohorts include:

- 1. Run-in Cohort (approximately 30 subjects)
- 2. Validation Cohort 1 (approximately 20 subjects)
- 3. Validation Cohort 2 (approximately 75 evaluable subjects)
- 4. Validation Cohort 3 (approximately 65 evaluable subjects)

After 75 evaluable subjects in the Validation 2 Cohort have been completed, an interim analysis will be conducted to compare results against the primary endpoint specification. If the primary endpoint has been achieved, the study will be terminated. If not, the trial will continue with enrolment into Validation Cohort 3 until 140 evaluable subjects are enrolled.

The population will be split into stratums in accordance with eGFR by the CKD-EPI equation (pre-2021):

- Stratum 1: 50% of subjects with an eGFR \geq 70 mL/min/1.73 m²
- Stratum 2: 50% of subjects with an eGFR < 70 mL/min/1.73 m^2

Subjects will be targeted across the spectrum of eGFR from normal through Stage 4 CKD. Subjects with an eGFR > 120 mL/min/1.73 m² or < 15 mL/min/1.73 m² will be excluded. Efforts will be made to balance enrollment across the following eGFR levels such that each subcategory has at least 6 subjects enrolled:

- $\geq 90 \leq 120 \text{ mL/min}/1.73 \text{ m}^2$
- $\overline{60} 89 \text{ mL/min}/1.73 \text{ m}^2$
- 45 59 mL/min/1.73 m²
- 30 44 mL/min/1.73 m²
- 15 29 mL/min/1.73 m²

Approximately 50% of subjects within each stratum enrolled in the US will be Fitzpatrick Skin Scale (FSS) I-III and 50% of subjects will have FSS IV-VI. Subjects will be targeted across the full spectrum of FSS (I – VI) such that FSS cohorts I-II, III-IV and V-VI will each enroll no less than 6 subjects.

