6.12 Repeat Subjects

Subjects may be re-enrolled in the protocol in the following situations (and if no documented safety concerns regarding exposure to the investigational device or drug):

- If they were part of the Run-in Cohort and/or Validation Cohort 1
- When a dose extravasation has occurred
- When there is a device malfunction (sensor falling off during the monitoring period and before a tGFR has been reported)
- If no tGFR is reported due to another issue
- Back-up subjects who were not dosed

Stratum 1 subjects must have a minimum of a 3-day wash-out from prior exposure of MB-102 before receiving another dose. Stratum 2 subjects must have a minimum of a 5-day wash-out from prior exposure of MB-102 before receiving another dose.

In some cases, the screening visit (if outside the 28-day window) may need to be repeated. Repeat subjects enrolled into Validation Cohort 2 or 3 will be provided with a new subject ID, however the original subject ID will be cross-referenced in the database.

Subjects can be in the study a maximum of four times and only when the above situations have occurred. Subjects who successfully complete Validation Cohort 2 with full PK and an average session TGFR cannot repeat the study.

7 Efficacy and Safety Variables

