9.7 Determination of Sample Size

For a P30 true value of 0.95, alpha of 0.025, performance goal of 85%, power of 90%, the one-sided exact binomial test yields a sample size of 102.

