3.1 Primary Objective and Endpoint

The primary objective is to establish that MB-102 transdermal fluorescence measured GFR using the MediBeacon[®] Transdermal GFR Measurement System is comparable to the measured MB-102 indexed plasma GFR.

The primary endpoint is the performance measure of P30 for transdermal-derived GFR with respect to the plasma-derived indexed GFR, with a 95% confidence interval. The performance goal is 85%. Success for the study will be that the lower limit of the 95% CI is greater than 85%.

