8.2 Sample Size Determination

The One-Sample Proportion Test is used to calculate the sample size. The required sample size was calculated assuming the true proportion is 0.95, the test is one-sided exact binomial, $\alpha = 0.025$, and the power is $1 - \beta = 0.90$. The P30 sample size calculation yields 102 subjects. However, to remain consistent with the previous sample size from the pivotal study (protocol 100-003) for the TGFR, the study will enroll 140 evaluable subjects.

Statistical Analysis Plan		Page 26 of 29
MediBeacon Inc.	An Open Label, Multi-Center, Safety and Pharmacokinetic Bridging Study of MB-102 (Relmapirazin) and the Use of the MediBeacon [®] Transdermal GFR Measurement System using the TGFR Reusable Sensor with Disposable Adhesive Ring in Normal and Renal Compromised Subjects for the Evaluation of Kidney Function	Ver 4.0

An adaptive trial design will be employed for the reusable sensor as follows:

- 1. Run-in cohort of up to 30 evaluable subjects will commence the study. Additional Run-in subjects may be enrolled at new clinical sites to ensure protocol compliance. Run-in subject data will be considered tuning data.
- 2. Validation Cohort 1 (approximately 20 evaluable subjects) will be used to confirm final algorithm selection. Validation Cohort 1 subject data will be considered tuning data.
- 3. Validation Cohort 2 (approximately 75 evaluable subjects) will be analyzed in an interim analysis to compare results against the primary endpoint specification. At that time, the primary endpoint null hypothesis will be tested using an exact binomial test at a one-sided nominal alpha level of 0.0150 using the method of Pocock for a two-stage design with the interim analysis performed based on the first 53.57% of the planned number of subjects. At the final analysis, the primary endpoint null hypothesis will also be tested at a one-sided nominal alpha level of 0.0150. This will control the overall Type I error rate at the one-sided 0.025 level.
- 4. If the primary endpoint has been achieved, the study will be terminated. If not, the trial will be continued.
- 5. Validation Cohort 3 (approximately 65 evaluable subjects) will be enrolled in the event the interim analysis did not meet the primary outcome measure. Final analysis will be of the 140 evaluable subjects.

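### The primary P30 counts only sessions in which the device reported a tGFR, so alone it cannot show the effectiveness of the system with the new sensor and ring

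*SAP*

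**What the plan says.** SAP 8.1 and Protocol 9.2 define the Intent-to-Measure set as subjects "for whom an average session tGFR or an average snapshot tGFR* has been calculated" who also had no major deviation affecting system performance. The mITM set is the ITM set without PK outliers, and it is the primary set for every effectiveness analysis. SAP 8.1 limits both sets to Validation Cohorts 2 and 3.

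Protocol 5.4.1 states: "Unevaluable subjects are those with major protocol deviations that impact efficacy (such as no reported average session tGFR, premature sensor removal, extravasations, etc". Protocol 10.5 lists failure to obtain an average session or snapshot value, and removal of the sensor before a tGFR, among the major deviations. Protocol 5.4.5 and one sentence of SAP 2.3 permit replacement. A second sentence of SAP 2.3 is unconditional, up to the cap of 240 enrolled. Protocol 6.12 allows the same person to re-enrol in several situations, including: "When there is a device malfunction (sensor falling off during the monitoring period and before a tGFR has been reported". It also allows this when no tGFR was reported for another reason. A person may be in the study at most four times.

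Nothing is imputed (Protocol 9.8, SAP 8.4). No section counts a missing tGFR as a failure.

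**The concern.** The study bridges to a reusable sensor with a clip-on disposable ring, and one of its two objectives (Protocol 4, SAP 2.1) is the safety and effectiveness of the system with that sensor and ring. Attachment is the part that changed. Under Protocol 5.5.1, a sensor that comes off after injection is not replaced, and a sensor applied while MB-102 is in the body cannot measure. A dosed subject who loses the sensor before a value appears therefore gets no GFR from that session.

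The plan removes exactly those sessions before P30 is computed and can fill the place with another subject, or with a later session of the same subject. The name of the set suggests that everyone in whom measurement was intended is counted, which is not so. Two systems with the same accuracy among reported values, one that almost always reports and one that often does not, would have the same chance of meeting the primary endpoint, provided the evaluable numbers are reached.

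**Working it through.** **Inputs.** The planning values are in Protocol 9.7: "For a P30 true value of 0.95, alpha of 0.025, performance goal of 85%, power of 90" per cent, with the statement that "the one-sided exact binomial test yields a sample size of 102". Each look is tested at a "one-sided nominal alpha level of 0.0150 using the method of Pocock for a two-stage design" (SAP 8.2), at 75 and at 140 evaluable subjects. Enrolment is capped at 240. Tuning takes about 30 run-in and 20 Validation Cohort 1 subjects. The documents give no no-result rate, so any such rate below is an assumption.

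**1. The plan's own figure.** Under the exact binomial with null 0.85, the critical count at n = 102 is 94: P(X ≥ 94 | 102, 0.85) = 0.0231 and P(X ≥ 94 | 102, 0.95) = 0.930. Power first reaches 0.90 at n = 93 but falls below it again from 95 to 101. From 102 on it stays at or above 0.90 (checked to n = 160). The stated 102 reproduces.

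**2. The planned rule at the final look.** P(X ≥ 128 | 140, 0.85) = 0.0170 and P(X ≥ 129 | 140, 0.85) = 0.0083, so 129/140 is the smallest passing result at 0.0150. No term in this rule depends on how many sessions gave no value.

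**3. Adding k device no-results as misses.** The p-value becomes P(X ≥ r | 140 + k, 0.85).

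| Hits r | k | r/(140 + k) | p | Passes at 0.0150 |
|---|---|---|---|---|
| 133 | 0 | 133/140 = 95.0% | 0.0002 | yes |
| 133 | 5 | 133/145 = 91.7% | 0.0114 | yes |
| 133 | 6 | 133/146 = 91.1% | 0.0206 | no |
| 129 | 0 | 129/140 = 92.1% | 0.0083 | yes |
| 129 | 1 | 129/141 = 91.5% | 0.0157 | no |

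Six no-results in 146 sessions is 4.1%. SAP 3.1 words success differently: "Success for the study will be that the lower limit of the 95% CI is greater than 85" per cent. On that plain 95% limit each reversal takes one more no-result (133/147, lower limit 84.5%; 129/142, lower limit 84.9%).

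**4. How many losses the cap allows.** 240 − 50 = 190 places for 140 evaluable subjects, so at most 190 − 140 = 50 losses, or 50/190 = 26.3%, from all causes together.

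**5. Where the share of accurate results crosses 85%.** Assume that 95% of reported values are accurate and that reporting is independent of accuracy. With a device no-result proportion L, the share of measured attempts with an accurate result is 0.95 × (1 − L). This is below 0.85 when L > 1 − 0.85/0.95 = 10.5%.

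**6. What the planned tables would show.**
- SAP 7.6 tabulates malfunctions in the style of adverse events. No denominator of measurement attempts is stated.
- SAP 8.4 reports the number of evaluable observations, without cause.
- SAP 8.8 gives each analysis set as a percentage of enrolled subjects. Read literally, that denominator includes the tuning cohorts, which SAP 8.1 keeps out of ITM and mITM. The mITM set also loses PK outliers.
- Repeat subjects in Validation Cohorts 2 and 3 get a new ID (Protocol 6.12), so counts by ID describe sessions rather than people.

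None of these isolates device no-results, gives an interval or stands beside P30.

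**The case against.** The strongest reply is that P30 given a reading is the endpoint the sponsor chose. The primary objective in SAP 3.1 is comparability of tGFR with indexed plasma GFR. That is paired agreement, which is undefined without a tGFR. After dislodgement, PK sampling also stops (Protocol 7.1.2.5.1), so the reference is usually incomplete as well. Scoring such a session as a miss measures reporting and accuracy together, which is a different quantity. This stands, and it is why the primary analysis should not change. A reader might infer that the primary test is invalid or its type I error compromised; the documents do not support that.

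The losses are also not hidden. Besides the tables above, Protocol 7.1.2.5 requires malfunctions and adhesive failures to be recorded, and Protocol 10.5 makes a missing tGFR a major deviation. Sessions with gaps under 30 minutes that yield a snapshot value are kept. What is missing is a no-result proportion by cause, an interval and a link to P30.

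Three further inferences go too far:
- **26% as a device failure rate.** The 50 places must also absorb extravasations, other major deviations, PK outliers, extra run-in subjects at new sites and unevaluable tuning subjects.
- **One no-result sinking the study at the interim.** 71/75 does become 71/76 (p = 0.0212), but 71 is the smallest passing count at 75 (70/75 gives p = 0.0234), and missing at the interim only continues the trial to 140.
- **Four device failures per person by design.** The limit of four also covers tuning-cohort repeats, extravasations and back-up subjects who were never dosed.

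Protocol 3.1 and 5.5 also say that light source, detector and sensing are unchanged, so only failures of attachment are clearly tied to the new design.

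**Conclusion.** The point holds as a limit on what the primary result can support. P30 in mITM answers how well tGFR agrees with plasma GFR when the system reports a value. It does not answer how often a dosed subject obtains an accurate value, and no other planned effectiveness analysis does.

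The size cannot be fixed from the documents. At the final analysis, a handful of no-results would separate the two questions: six on top of 133/140, or one on top of 129/140. The 10.5% crossing point rests on the assumed 95% accuracy and independence of reporting from accuracy. It also borrows the 85% goal, which the plan sets for P30 and not for this combined share. If device no-results prove rare, the supportive figure will sit close to the primary and strengthen it.

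**What to change.** Keep P30 in mITM as the primary analysis, with the same tests and sample size. In SAP 4 and 8.1, pre-specify one supportive analysis:

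- **Set.** Validation Cohort 2 and 3 subjects, using each person's first dosed session in those cohorts, linked through the cross-referenced IDs. Include the mITM subjects plus those whose session gave no average session or snapshot tGFR for a sensor or device reason: dislodgement, detachment, malfunction or no value reported.
- **Scoring.** Count the added sessions as not within 30%.
- **Left out.** Dosing extravasations, and the SAP 5.4 PK-outlier and nGFR above 120 exclusions as in the primary, so that dosing and reference-method errors are not charged to the device.
- **Cause.** Assign it from the recorded deviation and malfunction forms before P30 is computed.
- **Reporting.** Beside P30, give the no-result proportion among dosed first sessions in Validation Cohorts 2 and 3, by cause, with an exact 95% interval.

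The cost is SAP wording and one extra table from data already collected. The supportive figure will be less favourable than the primary, and it does not enter the success rule.

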2.2 Number of Planned Sites and Subjects

This study will take place at up to 5 investigational sites in the US.

	Statistical Analysis Plan	Page 7 of 29
MediBeacon Inc.	An Open Label, Multi-Center, Safety and Pharmacokinetic Bridging Study of MB-102 (Relmapirazin) and the Use of the MediBeacon [®] Transdermal GFR Measurement System using the TGFR Reusable Sensor with Disposable Adhesive Ring in Normal and Renal Compromised Subjects for the Evaluation of Kidney Function	Ver 4.0

Up to 240 subjects are planned for enrollment. The population will be split into stratums in accordance with screening eGFR measured by the CKD-EPI equation (pre-2021):

- Stratum 1: 50% of evaluable subjects with an eGFR \ge 70 mL/min/1.73 m²
- Stratum 2: 50% of evaluable subjects with an eGFR < 70 mL/min/1.73 m² Approximately 50% of subjects within each Stratum enrolled will be Fitzpatrick skin scale (FSS) I-III and 50% of subjects will have FSS IV-VI. Subjects will be enrolled across a spectrum of both eGFR (15 mL/min/1.73 m2) and FSS.

Subjects will be screened and if deemed eligible, will be enrolled. Subjects will be considered enrolled in the study after

- Signing the study specific informed consent form
- Receiving the sensor, and
- Receiving the MB-102 injection

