3.3 Safety Evaluation

Safety of MB-102 will be evaluated through treatment emergent adverse events (TEAEs), where treatment emergence is defined with respect to the first administration of MB-102.

Safety of the MediBeacon® Transdermal GFR Measurement System will be evaluated through TEAEs, where treatment emergence is defined with respect to the start time of device use. Additional safety variables include physical examinations, clinical laboratory assessments, ECGs, and concomitant medication use. All clinically significant findings in physical examinations, clinical laboratory assessments and ECGs will be reported as an AE or as medical history (if observations are noted prior to dose administration).

Statistical Analysis Plan		Page 12 of 29
MediBeacon Inc.	An Open Label, Multi-Center, Safety and Pharmacokinetic Bridging Study of MB-102 (Relmapirazin) and the Use of the MediBeacon [®] Transdermal GFR Measurement System using the TGFR Reusable Sensor with Disposable Adhesive Ring in Normal and Renal Compromised Subjects for the Evaluation of Kidney Function	Ver 4.0

4 Analysis of Primary Endpoint

The primary endpoint is the performance measure of P30 for transdermal-derived GFR with respect to the plasma-derived indexed GFR, with a 95% confidence interval. The performance goal is 85%. Success for the study will be that the lower limit of the 95% CI is greater than 85%.

The primary endpoint will be calculated for subjects enrolled into the Validation 2 and 3 (if applicable) cohorts only. The Run-in cohort and Validation 1 cohort enrollment were performed to provide final tuning data and used for software updates.

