Significant findings that were noted to be present at or prior to dosing must be included in the relevant medical history page of the eCRF. Significant new findings that begin or worsen after dosing must be recorded on the AE page of the eCRF. Subjects should be followed until the event is resolved or stabilized. AEs are collected from the time of initial sensor placement until the completion of the follow-up visit.

All reported TEAEs, including unanticipated adverse device effects (UADE), and serious adverse events (SAE) will be summarized for all enrolled subjects. The overall numbers and percentages of subjects who experienced any TEAEs will be presented. In addition to the TEAEs, description of all TEAEs, including description/term of the symptom event (underlying diagnosis), the date of first occurrence and date of resolution (if applicable), classification of serious or not serious, severity, causal relationship, action taken, and event outcome will be listed. TEAEs will also be summarized at the subject level by system organ class and preferred term, and at the event level by system organ class/preferred term and severity and by system organ class/ preferred term and relationship to treatment.

In addition to the events reported as AEs, the parameters of clinical laboratory tests including clinical chemistry, hematology, urinalysis and coagulation parameters will be summarized using the descriptive

Statistical Analysis Plan		Page 23 of 29
MediBeacon Inc.	An Open Label, Multi-Center, Safety and Pharmacokinetic Bridging Study of MB-102 (Relmapirazin) and the Use of the MediBeacon [®] Transdermal GFR Measurement System using the TGFR Reusable Sensor with Disposable Adhesive Ring in Normal and Renal Compromised Subjects for the Evaluation of Kidney Function	Ver 4.0

statistics. Clinical laboratory analytes are presented in **Table 1**. More information on descriptive statistics is presented in **Section 8.6**.

ECG data will be listed. Concomitant medications, coded using the World Health Organization (WHO) drug dictionary, administered within 3 days prior to MB-102 dose administration and through the follow-up study visit will be also listed. Furthermore, concomitant non-drug therapies will be listed.

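### Device adverse events count from sensor placement, but every safety summary requires the MB-102 injection, so a subject who wore the sensor and was never injected is left out

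*SAP*

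**What the plan says.** Start of observation for the device:

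- For the measurement system, SAP 3.3 states that "treatment emergence is defined with respect to the start time of device use". Protocol 9.6 specifies this as placement of the sensor on the skin.
- AE collection begins at sensor placement (Protocol 7.1.2 and Table 2 notes; SAP 7).
- The sensor is worn for a baseline acquisition of about 20 to 30 minutes before dosing (Protocol 6.5). The Table 2 notes require at least 15 minutes.

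Who is summarised:

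- SAP 8.1: "The safety population will consist of all subjects who are enrolled in the study and have been dosed with MB-102". Protocol 9.2 has the same definition.
- SAP 8.1 also says: "The Safety Population will be used for the analysis of all safety variables and baseline characteristics".
- SAP 7: "All reported TEAEs, including unanticipated adverse device effects (UADE), and serious adverse events (SAE) will be summarized for all enrolled subjects".
- SAP 2.2 lists three conditions for being enrolled: signed consent, the sensor, and "Receiving the MB-102 injection".
- Protocol 9.6 closes by confining all safety analyses to subjects who receive a dose of MB-102.

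Neither document defines a set based on device exposure.

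**The concern.** The clock for device safety starts at the sensor, but entry to every safety summary is decided by a later event, the injection. Someone who had the sensor applied and did not go on to the injection has been exposed to the device and can have a device-related event, yet belongs to no analysis set.

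Safety of the system with the reusable sensor and disposable adhesive ring is a stated objective (Protocol 4, SAP 2.1). Protocol 3.3 and 8.2 attribute past device-related events to the adhesive or the means of attachment, and these need no drug. If a subject stops because of an early skin reaction or a sensor problem, the device event itself causes the exclusion. In that case the omission favours the device.

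**Working it through.** The check is mainly one of definitions. Take a subject who signs consent, has a sensor placed, and is never injected.

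1. Is the subject under device observation? Yes. Device treatment emergence and AE collection have both begun (Protocol 7.1.2 and 9.6; SAP 3.3 and 7).
2. Is the subject in the Safety Population? No, because dosing is required (Protocol 9.2; SAP 8.1).
3. Is the subject enrolled for the purpose of SAP 7? No, because SAP 2.2 requires the injection. Protocol 5.1 uses the word more loosely, for eligible subjects after screening. That does not help: Protocol 9.2 and 9.6 impose dosing anyway, and SAP 1 says the SAP prevails where the two differ.
4. Does disposition show the subject? No row is specified, and percentages use the number enrolled (Protocol 9.3; SAP 8.8).

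The gap therefore follows from the text on every route. It does not depend on how the event is recorded, since it remains even if every pre-dose reaction is entered as an AE.

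The documents state no figure for the size of this group, so what follows is illustration.

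- Dosed subjects: 240, the enrolment cap (Protocol 5.4.1; SAP 2.2).
- Device event rate in the dosed: 3%, an assumption close to Pilot 2, where 7 of 234 subjects had device-related events (Protocol 8.1): 7/234 = 3.0%. This gives 0.03 × 240 = 7.2 events.
- k = subjects with a sensor and no injection, assumed 1, 5 or 10.
- x = how many of those k have a device event.

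Share left out = k/(240 + k). Rate in all sensor wearers = (7.2 + x)/(240 + k).

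| k | share left out | x = 0 | x = 1 | x = k |
|---|---|---|---|---|
| 1 | 1/241 = 0.4% | 7.2/241 = 3.0% | 8.2/241 = 3.4% | 3.4% |
| 5 | 5/245 = 2.0% | 7.2/245 = 2.9% | 8.2/245 = 3.3% | 12.2/245 = 5.0% |
| 10 | 10/250 = 4.0% | 7.2/250 = 2.9% | 8.2/250 = 3.3% | 17.2/250 = 6.9% |

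The rate rises only if x/k exceeds 3%. If the added subjects react at the same 3%, it does not change: for k = 10, (7.2 + 0.3)/250 = 3.0%.

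**The case against.** The strongest reply is that the documents describe no pre-dose device problem that ends without dosing. If the sensor dislodges during baseline, Protocol 5.5.1 allows a new sensor and a re-start, and 7.1.2.5.1 provides for a new ring and a re-started baseline. A subject handled that way and then injected is in the Safety Population, with device events counted from sensor placement. This stands, and it is why the group is probably small. But the re-start is permitted, not assured. Protocol 6.5 also allows the dosing catheter to be placed after the baseline and notes that this can be hard in older subjects. Non-dosing after sensor placement is thus possible, but it is an inference and not a documented event.

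Four stronger readings are tempting, and the documents do not carry them:

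- **The undosed group is already named.** Protocol 6.12 lists "Back-up subjects who were not dosed" among those who may re-enrol. Nothing says they wore a sensor.
- **Device results are biased in the device's favour.** Undosed subjects also enlarge the denominator. Their wear may be only the 20 to 30 minute baseline, against at least 12.5 hours in Stratum 1 (Protocol 5.5), so including them may lower the rate. Only exclusion caused by a device event has a clear direction. A reader might move 7/240 (2.9%) to 9/242 (3.7%) by adding two subjects, but that assumes both react.
- **Malfunctions are lost too.** SAP 7.6 names no population. It says only that malfunctions are presented much as adverse events are, and Protocol 7.1.2.5 records all of them in the eCRF.
- **Serious events would go unseen.** SAE and UADE reporting (Protocol 7.1.2.3) and Safety Review Committee review (Protocol 7.2, SAP 7.1) do not depend on the Safety Population. The AE listings in SAP 10 name no population either.

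**Conclusion.** The concern holds as a mismatch of definitions. By the plan's own rules a subject is device-exposed from sensor placement, yet a never-injected subject is outside the device TEAE and UADE summaries and their denominators. This includes a subject for whom a device event was the reason for not proceeding.

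The size is unknown. The 0.4% to 4.0% share rests on an assumed 1 to 10 such subjects against 240 dosed. The effect on the rate has no fixed direction, and at equal rates there is none. The primary endpoint, MB-102 safety, event capture and expedited reporting are unaffected by this definition. The point is minor and worth correcting because the correction is cheap.

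**What to change.** - In SAP 8.1 and Protocol 9.2, define a Device Safety Set: all consented subjects with a sensor placed, dosed or not. Use it for device TEAEs and UADEs.
- Keep the dosed Safety Population for MB-102 TEAEs.
- In SAP 7.6, state that malfunctions use the Device Safety Set.
- In SAP 7, replace the reference to enrolled subjects with the matching set, and reword the closing restriction in Protocol 9.6 to agree.
- In the disposition table, report the number with a sensor placed and no injection.

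The cost is some wording and one more denominator. AE collection already starts at sensor placement. The drawback is that undosed subjects have shorter sensor wear, and the 7 ± 3 day visit is timed from dosing, so they have no follow-up anchored in that way. Protocol 6.11 lists early-withdrawal assessments that could apply to them. Show them as a separate row so that unequal exposure and follow-up are visible. If there are none, the results do not change and the report can say so.
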